9.5.1.4.2 SERIOUS ADVERSE EVENTS AND EVENTS ASSOCIATED WITH SPECIAL SITUATIONS

An SAE is any untoward medical occurrence that at any dose:

- Results in death
- Is life-threatening (ie, the subject was at immediate risk of death from the AE as it occurred; this does not include an event that, had it occurred in a more severe form or was allowed to continue, might have caused death)
- Requires inpatient hospitalization or prolongation of existing hospitalization
- Results in persistent or significant disability/incapacity
- Is a congenital anomaly/birth defect (in the child of a subject who was exposed to the study drug)

Other important medical events that may not be immediately life-threatening or result in death or hospitalization but, when based on appropriate medical judgment, may jeopardize the subject or may require intervention to prevent one of the outcomes in the definition of SAE listed above should also be considered SAEs. Medical and scientific judgment should be exercised in deciding whether expedited reporting is appropriate in such situations.

Refer to [Section 9.5.1.4.3](#) for the list of study-specific events to be reported as SAEs.

In addition to study-specific events, events associated with special situations include pregnancy or exposure to study drug through breastfeeding; AEs associated with study drug overdose, misuse, abuse, or medication error. These events associated with special situations are to be captured using the SAE procedures but are to be considered as SAEs only if they meet one of the above criteria. All AEs associated with special situations are to be reported on the CRF whether or not they meet the criteria for SAEs.

All SAEs must be followed to resolution or, if resolution is unlikely, to stabilization.

The following hospitalizations are not considered to be SAEs because there is no “adverse event” (ie, there is no untoward medical occurrence) associated with the hospitalization:

- Hospitalizations for respite care
- Planned hospitalizations required by the protocol
- Hospitalization planned before informed consent (or assent) (where the condition requiring the hospitalization has not changed after study drug administration)
- Hospitalization for administration of study drug or insertion of access for administration of study drug
- Hospitalization for routine maintenance of a device (eg, battery replacement) that was in place before study entry

If possible, a blood sample for the measurement of study drug plasma concentration should be drawn at the first report of an SAE or a severe unexpected AE and at its resolution.

9.5.1.4.3 STUDY-SPECIFIC ADVERSE EVENTS

The following study-specific AEs will be considered as always serious as an important medical event, in the absence of other seriousness criteria: serotonin syndrome, psychosis, suicidal behavior, priapism, new or worsened valvular heart disease, new or worsened pulmonary hypertension, new arrhythmia or conduction abnormality, severe symptomatic hypoglycemia, and malignant neoplasms. The definitions of these study-specific AEs and the instructions for reporting are described in [Section 9.5.4.3.3](#).

9.5.1.4.4 LABORATORY MEASUREMENTS

Clinical laboratory tests to be performed, including hematology, chemistry, and urinalysis, are summarized in [Table 2](#). Subjects should be in a seated position during blood collection.

The Schedule of Procedures/Assessments ([Table 3](#)) shows the visits and time points at which blood for clinical laboratory tests and urine for urinalysis will be collected in the study.

Table 2 Clinical Laboratory Tests

Category	Parameters
Hematology	Hematocrit, hemoglobin, platelets, RBC count, and WBC count with differential (bands, basophils, eosinophils, lymphocytes, monocytes, neutrophils)
Chemistry	
Electrolytes	Calcium, chloride, potassium, sodium
Liver function tests	Alanine aminotransferase, alkaline phosphatase, aspartate aminotransferase, gamma glutamyl transpeptidase, direct bilirubin, total bilirubin
Renal function tests	Blood urea/blood urea nitrogen, creatinine
Other	Albumin, cholesterol, globulin, glucose, lactate dehydrogenase, phosphorus, total protein, triglycerides, uric acid
Urinalysis	Bacteria, casts, crystals, epithelial cells, glucose, ketones, occult blood, pH, protein, RBCs, specific gravity, WBCs

RBC = red blood cell, WBC = white blood cell.

Clinical laboratory tests during the study will be performed by a central laboratory. All blood and urine samples will be collected and sent to the central laboratory on the day of collection unless otherwise instructed.

A laboratory abnormality may meet the criteria to qualify as an AE as described in this protocol (see [Section 9.5.1.4.1](#) and the CRF Completion Guidelines). In these instances, the AE corresponding to the laboratory abnormality will be recorded on the Adverse Event CRF (see [Section 9.5.4.3.2](#)).

9.5.1.4.5 VITAL SIGNS AND WEIGHT MEASUREMENTS

Vital sign measurements (ie, systolic and diastolic blood pressure [mmHg], pulse [beats per minute], respiratory rate [per minute], body temperature [in centigrade], and weight [kg]) will be obtained at the visits designated in the Schedule of Procedures/Assessments ([Table 3](#)) by a validated method. Blood pressure and pulse will be measured after the subject has been sitting for 5 minutes. All blood pressure measurements should be performed on the same arm, preferably by the same person.

9.5.1.4.6 PHYSICAL EXAMINATIONS

Physical examinations (comprehensive or symptom directed) will be performed as designated in the Schedule of Procedures/Assessments ([Table 3](#)). A comprehensive physical examination will include evaluations of the head, eyes, ears, nose, throat, neck, chest

(including heart and lungs), abdomen, limbs, and skin. A urogenital examination will only be required in the presence of clinical symptoms related to this region. Documentation of the physical examination will be included in the source documentation at the site. Significant findings at the Screening Visit will be recorded on the Medical History and Current Medical Conditions CRF. Changes from screening physical examination findings that meet the definition of an AE will be recorded on the Adverse Events CRF.

9.5.1.4.7 NEUROLOGICAL EXAMINATION

Neurological examination will consist of assessment of mental status, sensory systems, cranial nerves, motor function, deep tendon reflexes, and cerebellar functions.

9.5.1.4.8 ELECTROCARDIOGRAMS

ECGs will be obtained as designated in the Schedule of Procedures/Assessments ([Table 3](#)). If subject has a normal ECG baseline reading, but during any visit thereafter the QT is measured as more than 460 ms, 3 consecutive ECGs separated by 5 to 10 minutes will be performed to confirm the abnormality.

An ECG abnormality may meet the criteria of an AE as described in this protocol (see [Section 9.5.1.4.1](#)) and the CRF Completion Guidelines. In these instances, the AE corresponding to the ECG abnormality will be recorded on the Adverse Events CRF.

9.5.1.4.9 ECHOCARDIOGRAMS

Echocardiograms will be obtained as designated in the Schedule of Procedures/Assessments ([Table 3](#)).

In this study, echocardiographic images will be acquired as part of safety assessments. Standardized training will be provided for all echocardiographers, and centralized procedures for collecting, analyzing, and reporting echocardiographic data will be implemented. All echocardiograms will be over-read by 2 blinded central readers (primary and secondary). The baseline echocardiograms will be performed before randomization between Visits 1 and 2 for subjects who are considered otherwise eligible for the study based on initial review of eligibility criteria. Valvular regurgitation as assessed on echocardiogram will be rated absent, trace, mild, moderate, or severe for the aortic, mitral, tricuspid, and pulmonic valves. The evaluations will be based on the recommendations from the American Society of Echocardiography ([Zoghbi et al., 2017](#)). Pulmonary artery pressure will be estimated by a comprehensive approach that includes the tricuspid regurgitation jet velocity (if present), right ventricular outflow tract flow acceleration time, pulmonic regurgitation peak early diastolic velocity (if present), right ventricular outflow tract flow acceleration time, pulmonic regurgitation peak early diastolic velocity (if present), and the eccentricity index that describes the interventricular septum position at end-systole ([Jone and Ivy, 2014](#)).

9.5.1.4.10 OTHER SAFETY ASSESSMENTS

C-SSRS

An assessment of suicidality using the C-SSRS will be performed at Screening, Baseline, Day 1 postdosing, every visit, including after the last dose of study drug, and at the Termination Visit, as designated in the Schedule of Procedures/Assessments ([Table 3](#)).

Pregnancy Test

A serum β -hCG test will be performed for female subjects age 12 years old and above, or of child-bearing potential, only. A sample of blood will be taken at Screening; at all other time points a urine pregnancy test will be performed as specified in the Schedule of Procedures/Assessments ([Table 3](#)). If urine cannot be obtained for pregnancy testing after Screening, a serum pregnancy test will be performed.

9.5.1.5 Other Assessments

9.5.1.5.1 QUALITY OF LIFE IN EPILEPSY SURVEY

Quality of life will be assessed using Quality of Life in Epilepsy Survey (QOLIE-31). The QOLIE-31 is a survey of health-related quality of life for adults that includes 31 questions about subject's health and daily activities.

9.5.1.5.2 PEDIATRIC QUALITY OF LIFE INVENTORY

The Pediatric Quality of Life Inventory (PedsQL 4.0) is a modular instrument for measuring health-related quality of life in children and adolescents ages 2 to 18 years. Generic Core Scales are multidimensional child self-report and parent proxy-report scales developed as the generic core measure to be integrated with the PedsQL Disease-Specific Modules. The PedsQL 4.0 Generic Core Scales consist of 23 items applicable for healthy school and community populations, as well as pediatric populations with acute and chronic health conditions.

9.5.2 Schedule of Procedures/Assessments

9.5.2.1 Schedule of Procedures/Assessments

[Table 3](#) presents the Schedule of Procedures/Assessments for the Core Study.

Table 3 Schedule of Procedures/Assessments in Study E2023-A001-304: Core Study

Phase	Prerandomization	Randomization									
Period	Screening/Baseline	Treatment ^a							Follow-up ^{b,c}		
Visit	1	2	3	4	5	6	7	8		ED ^d	Unscheduled ^e
Week	From -4 Weeks to Week 0	0	1	2	4	6	10	14	4 weeks after the last dose		
Procedures/Assessments											
Demography	X										
Informed consent/assent	X										
Inclusion/exclusion criteria	X	X									
Medical history	X										
Epilepsy history ^f	X										
Prior and concomitant medications	X	X	X	X	X	X	X	X	X	X	X
Prior and concomitant AEDs	X	X	X	X	X	X	X	X	X	X	X
Adverse events	X	X	X	X	X	X	X	X	X	X	X
Randomization		X									
Study drug compliance			X	X	X	X	X	X		X	X ^{e,g}
Dispense study drug		X	X	X	X	X	X	X ^h			X ^{e,g}
Retrieve unused study drug			X	X	X	X	X	X		X	X ^{e,g}
Dispense subject's diary	X	X	X	X	X	X	X	X ^h			X ^e
Retrieve and review diary		X	X	X	X	X	X	X		X	X ^e
Neurological examination ⁱ	X							X		X	

Table 3 Schedule of Procedures/Assessments in Study E2023-A001-304: Core Study

Phase	Prerandomization	Randomization									
Period	Screening/Baseline	Treatment ^a							Follow-up ^{b,c}		
Visit	1	2	3	4	5	6	7	8		ED ^d	Unscheduled ^e
Week	From -4 Weeks to Week 0	0	1	2	4	6	10	14	4 weeks after the last dose		
Procedures/Assessments											
Physical examination ⁱ	X							X		X	
Vital signs, and weight	X	X	X	X	X	X	X	X		X	X ^e
Height	X										
Clinical laboratory tests ^j	X					X		X		X	X ^{e,k}
Serum β-hCG test ^l	X										
Urine pregnancy test ^l		X						X		X	X ^e
12-Lead ECG ^m	X							X		X	X ^{e,k}
Echocardiogram	X							X		X	X ^{e,k}
PK sampling (plasma) ⁿ			X	X	X	X				X ^o	
IxRS call	X	X	X	X	X	X	X	X		X	X ^e
C-SSRS	X	X	X	X	X	X	X	X		X	
QoL		X						X		X	
Clinical Global Impression ^p		X						X		X	

AE = adverse event, AED = antiepileptic drug, β-hCG = beta-human chorionic gonadotropin, COVID-19 = Coronavirus disease 2019,

C-SSRS = Columbia-Suicide Severity Rating Scale, ECG = electrocardiogram, ED = early discontinuation, IxRS = interactive voice and web response system,

Table 3 Schedule of Procedures/Assessments in Study E2023-A001-304: Core Study

Phase	Prerandomization	Randomization									
Period	Screening/Baseline	Treatment ^a							Follow-up ^{b,c}		
Visit	1	2	3	4	5	6	7	8		ED ^d	Unscheduled ^e
Week	From -4 Weeks to Week 0	0	1	2	4	6	10	14	4 weeks after the last dose		
Procedures/Assessments											

PedsQL = Pediatric Quality of Life Inventory, PK = pharmacokinetic, QoL = Quality of Life in Epilepsy Scale/Pediatric Quality of Life Inventory 4.0; QOLIE-31 = Quality of Life in Epilepsy Survey.

- a: All visits to be done within ± 3 days of the schedule. If any of the visits after Visit 1 are conducted remotely due to the COVID-19 pandemic, at a minimum, the following assessments should be conducted: AEs, suicidality assessment, concomitant medications, review of seizure diary data, and study drug compliance (any missed or extra doses with dates). Study drug and seizure diary may be picked up from the site by the subject/caregiver or shipped from the site to the subject's location. C-SSRS and Clinical Global Impression may be conducted remotely over the phone by a qualified rater and QOLIE-31 and PedsQL based on input from subject over the phone.
- b: Visit to be done within ± 7 days of the schedule.
- c: The Follow-up Visit only applies to those subjects who do not enter the Extension Phase after completion of this study.
- d: These assessments will be conducted for subjects who discontinue the study or treatment early for any reason after Visit 2.
- e: At Unscheduled Visits these assessments/procedures conducted if needed.
- f: Epilepsy history will include information on genetic mutation related to epilepsy, if available.
- g: Unused study drug to be retrieved and study drug dispensed only for subjects requiring dose change at Unscheduled Visits.
- h: Study drug and seizure diary will be dispensed only for subjects who enter the Extension Phase.
- i: Physical and neurological examinations will only be performed at the indicated visits. For all other clinic visits during the study, the physical and the neurological examinations will only be performed when there is a complaint from the subject. Clinically significant abnormal findings from the physical or the neurological examinations will be reported as AEs.
- j: Clinical laboratory tests include hematology, blood chemistry, and urinalysis.
- k: At Unscheduled Visits, these assessments will only be done if the results from the previous visit were deemed clinically significant by the investigator.
- l: Only for female subjects of child-bearing potential (defined as all postmenarche females, unless postmenopausal or have been sterilized surgically).
- m: If subject has a normal ECG baseline reading, but during any visit thereafter the QT is measured as >460 ms, 3 consecutive ECGs separated by 5 to 10 minutes will be performed to confirm the abnormality.
- n: One blood sample (approximately 1 mL) for determination of lorcaserin plasma concentrations will be collected at predose and between 1 to 2 hours postdose at Visit 4 and 6; 3 to 6 hours postdose only at Visit 5 and 7.

Table 3 Schedule of Procedures/Assessments in Study E2023-A001-304: Core Study

Phase	Prerandomization	Randomization									
Period	Screening/Baseline	Treatment ^a							Follow-up ^{b,c}		
Visit	1	2	3	4	5	6	7	8		ED ^d	Unscheduled ^e
Week	From -4 Weeks to Week 0	0	1	2	4	6	10	14	4 weeks after the last dose		
Procedures/Assessments											

o: At ED Visit, 1 blood sample (approximately 1 mL) PK samples should only be collected only if can be drawn within 50 hours of the last dose of study drug.

p: Clinical Global Impression of Severity is conducted At Visit 2, and Clinical Global Impression of Change at Visit 8 or ED.

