9.3.3 Removal of Subjects From Therapy or Assessment

The investigator may withdraw the subject from the study at any time for safety or administrative reasons. The subject may stop study drug or withdraw from the study at any time for any reason.

The reason for discontinuation will be documented. If a subject discontinues study treatment, the subject will enter the Follow-Up Period and complete protocol-specified off-treatment visits and procedures. The investigator should confirm whether a subject will withdraw from study treatment but agree to continue protocol-specified, off-treatment study visits, procedures, or whether the subject will withdraw from the study. If a subject or guardian/legally authorized representative withdraws consent (or assent), the date will be documented in the source documents.

A subject who discontinues study treatment should be followed for subsequent protocol-specified visits and procedures. If a subject discontinues study drug but remains in the study, the set of end-of-treatment procedures, Early Treatment Discontinuation according to Early Discontinuation Visit schedule, will be administered, and further information will be collected at visits according to regular Schedule of Procedures/Assessments. The primary reason for discontinuation and all other reasons contributing to the subject’s discontinuation from study drug will be collected. If a subject discontinues from study treatment and the study at the same time, Early Discontinuation Visit will be conducted followed by safety Follow-up Visit (see [Section 9.5.5](#)).

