- d: These assessments will be conducted for subjects who discontinue the study or treatment early for any reason after Visit 9.
- e: At Unscheduled Visits these assessments/procedures conducted if needed.
- f: Unused study drug to be retrieved and study drug dispensed only for subjects requiring dose change at Unscheduled Visits.
- g: Physical and neurological examinations will only be performed at the indicated visits. For all other clinic visits during the study, the physical and the neurological examinations will only be performed when there is a complaint from the subject. Clinically significant abnormal findings from the physical or the neurological examinations will be reported as AEs.
- h: Clinical laboratory tests include hematology, blood chemistry, and urinalysis.
- i: At Unscheduled Visits, these assessments will only be done if the results from the previous visit were deemed clinically significant by the investigator.
- j: Only for female subjects of child-bearing potential (defined as all postmenarche females, unless postmenopausal or have been sterilized surgically).
- k: If subject has a normal ECG baseline reading, but during any visit thereafter the QT is measured as >460 ms, 3 consecutive ECGs separated by 5 to 10 minutes will be performed to confirm the abnormality.

Table 4 Schedule of Procedures/Assessments in Study E2023-A001-304: Extension Phase

Phase	Extension							
Period	Treatment ^a					Follow-up ^{b,c}		
Visit	9	10	11	12	13		ED ^d	Unscheduled ^e
Week	15	17	20	23	26	4 weeks after the last dose		
Procedures/Assessments								

l: Clinical Global Impression of Change at Visit 13 or ED.

m: One blood sample (approximately 1 mL) for determination of lorcaserin plasma concentration will be collected at predose and between 1 to 2 hours postdose at Visit 9, 11, and 13; 3 to 6 hours postdose only at Visit 10 and 12.

n: At ED, 1 blood sample (approximately 1 mL) PK samples should be collected only if samples can be drawn within 50 hours of the last dose of study drug.

Statistical Methods

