5.6.5 Electrocardiograms

ECG assessments will be performed at Unscheduled visit, if needed. Descriptive statistics for ECG parameters and changes from baseline will be presented by visit and treatment group. Proportion of subjects with New FDA-defined valvulopathy will be summarized by visit and treatment group.

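### Table 3 footnote k and Table 4 footnote i limit unscheduled laboratory, ECG and (Core Study) echocardiogram testing to follow-up of the previous visit's results, which conflicts with the if-needed rule on the same cells and leaves out new symptoms

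*Protocol*

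**What the plan says.** In Table 3 (Protocol 9.5.2.1) the Unscheduled cells for laboratory tests, ECG and echocardiogram each carry two footnotes. Footnote e is the general rule for the column: "At Unscheduled Visits these assessments/procedures conducted if needed". Footnote k then adds: "At Unscheduled Visits, these assessments will only be done if the results from the previous visit were deemed clinically significant by the investigator".

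Table 4 (Appendix 2) marks its Unscheduled cells for laboratory tests and ECG in the same way. Its footnote i says that "these assessments will only be done if the results from the previous visit were deemed clinically significant by the investigator". Table 4 has no echocardiogram row.

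Other text bears on the same question:

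- Protocol 9.7.1.8.5 says unscheduled ECGs are done as needed and refers the reader to Table 3. SAP 5.6.5 repeats this without the reference: "ECG assessments will be performed at Unscheduled visit, if needed".
- Table 3 footnote i gives examinations a symptom trigger. Outside the marked visits, "the physical and the neurological examinations will only be performed when there is a complaint from the subject".
- Table 3 footnote d covers the Early Discontinuation (ED) visit, which includes all three tests: "These assessments will be conducted for subjects who discontinue the study or treatment early for any reason after Visit 2".

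**The concern.** Footnote k looks only at results already in hand. A symptom that begins after the previous visit is not a reason to test under it, however cardiac it sounds. A new complaint does prompt a physical or neurological examination in the same table.

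Take a subject on treatment who is seen unscheduled at Week 5 with new syncope. The previous visit was Visit 5 (Week 4), which had no ECG and no echocardiogram, so no result exists that could satisfy k.

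This matters because Protocol 9.5.1.4.3 makes new arrhythmia or conduction abnormality, new or worsened valvular heart disease, and new or worsened pulmonary hypertension always-serious events. Protocol 9.7.1.8 and SAP 5.6 plan incidence summaries of such findings. Protocol 9.5.1.4.9 gives echocardiograms standardized training and two blinded central readers. If some sites follow footnote e and others follow k, similar symptoms will lead to different in-study testing.

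**Working it through.** There is no figure in the plan to reproduce. The check sets the visit columns of Tables 3 and 4 against the footnotes.

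**Step 1. Which footnote governs the cell.** Footnote e is general. Footnote g narrows it for study drug: "study drug dispensed only for subjects requiring dose change at Unscheduled Visits". Footnote k has the same form, with an explicit restriction. If e prevailed over k, k would do no work. The specific rule is therefore the natural one to follow, and Protocol 11.2 asks for strict adherence. The text nonetheless puts both rules on one cell.

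**Step 2. Where each test is scheduled.**

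| Test | Core Study visits (Table 3) | Of Visits 2–7 | Extension visits (Table 4) | Of Visits 9–12 |
|---|---|---|---|---|
| ECG | 1, 8, ED | 0 of 6 | 13, ED | 0 of 4 |
| Echocardiogram | 1, 8, ED | 0 of 6 | no row | – |
| Laboratory tests | 1, 6, 8, ED | 1 of 6 | 13, ED | 0 of 4 |

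**Step 3. Whether k can be met on treatment before Week 14.** The scheduled visit before any such Unscheduled Visit is one of Visits 2 to 7. The answer depends on how the reference to the previous visit's results is read.

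| Reading | ECG | Echocardiogram | Laboratory tests | New-symptom trigger |
|---|---|---|---|---|
| Result of that test at the preceding visit (literal) | cannot be met | cannot be met | only when Visit 6 is the preceding scheduled visit | no |
| Most recent result of that test | cannot be met | possible | possible | no |
| Any significant result at the preceding visit | sometimes | sometimes | sometimes | no |
| Footnote e keeps full effect | yes | yes | yes | yes, but k is then idle |

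Notes to this table:

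- *Literal reading.* An earlier Unscheduled Visit does not help, because its own first ECG or echocardiogram would need the same trigger.
- *Most recent result, ECG.* The only earlier ECG is the screening one, and exclusion criterion 11 removes subjects with a clinically significant abnormality.
- *Most recent result, echocardiogram.* A notable baseline finding could qualify, since criterion 4 excludes valvulopathy only with a history of fenfluramine use. Criterion 9 (clinically significant cardiac disease) narrows this further.

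**Step 4. Extension.** Visits 9 to 12 schedule neither laboratory tests nor ECG. Read literally, footnote i can be met from a scheduled on-treatment result only while Visit 8 (Week 14) is the preceding visit, that is, before Visit 9 (Week 15).

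**Step 5. The exception.** After stopping treatment a subject has the ED tests and may stay in the study. Protocol 9.3.3 says: "A subject who discontinues study treatment should be followed for subsequent protocol-specified visits and procedures". An Unscheduled Visit directly after the ED visit can therefore satisfy k. This is why the impossibility in Step 3 is confined to subjects still on treatment.

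**The case against.** The best case against this point is that the protocol shows a broader intent. Footnote e sits on the same cells. Protocol 9.7.1.8.5 describes unscheduled ECGs as done when needed and cites Table 3 as its source, so the looser wording is the protocol's own and not a SAP departure. The QT rule in 9.5.1.4.8 speaks of a QT measured at any later visit, although only Visit 8 and ED schedule a later Core Study ECG. Section 9.5.4.3.2 expects unscheduled laboratory testing. SAP 8.3 has a rule for several echocardiograms in one window. All of this stands as evidence of intent, and it is why the point is a conflict of wording. It does not remove the restriction in k and i. The QT rule also starts from an ECG already taken, so it supplies no first trigger.

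Three stronger readings are tempting, and the documents do not support them:

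- *Symptomatic subjects are denied testing.* The footnotes govern study procedures. Section 9.5.1.4.1 foresees ECGs that the protocol does not require, and weekly hepatic repeats are required under 9.5.4.3.2.
- *Safety events drop out of the summaries.* A new arrhythmia or valve finding made in clinical care is still reported as an SAE under 9.5.4.3.3, and stopping treatment brings the ED tests. No loss of events is shown.
- *Central ECG reading is lost.* None is specified. Two blinded readers are documented for echocardiograms only. Section 9.5.1.4.9 applies over-reading to all echocardiograms without limiting it to scheduled ones, but it does not say that one obtained in clinical care enters that process.

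**Conclusion.** The point holds as a conflict between two rules on the same cells, with a practical gap if the stricter one is followed. Read literally, footnote k cannot be met for two of its three tests (ECG and echocardiogram) in a subject on treatment before Week 14. Neither k nor Table 4 footnote i names new symptoms as a trigger. The possible loss is uneven in-study testing of symptomatic subjects, mainly the centrally over-read echocardiogram.

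Severity is low. Care, reporting, QT and hepatic repeats, and ED testing are intact. SAP Section 7 records that the study is being terminated with 22 subjects randomized, so little conduct remains to benefit.

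The conclusion assumes that:

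- sites let the specific footnote override the general one;
- enrolled subjects met criterion 11, which matters only for the most-recent-result reading of ECG;
- Tables 3 and 4 as printed were in force.

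The documents give no number of unscheduled visits, so no count of affected subjects can be offered.

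**What to change.** Replace Table 3 footnote k with wording such as: *Unscheduled laboratory tests, ECG and echocardiogram are done when clinically indicated in the investigator's judgment, including for new symptoms or signs, or when the most recent available result of that test was clinically significant.* Use the same text in Table 4 footnote i without the echocardiogram, since Table 4 has no row for it.

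This reconciles k and i with footnote e, and for ECG with Protocol 9.7.1.8.5 and SAP 5.6.5. It keeps follow-up of a significant earlier result as one trigger among others.

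The cost is one reworded footnote in each of two tables, made through the change procedure in Protocol 11.1, and a few extra symptom-driven tests. No scheduled procedure is added and no analysis changes.
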